##### 11.4.3.2. Severity

The severity of AEs and SAEs will be graded as follows:

- **Mild:** The event is easily tolerated by the patient and does not affect the patient's usual daily activities
- **Moderate:** The event causes the patient more discomfort and interrupts the patient's usual daily activities
- **Severe:** The event is incapacitating and causes considerable interference with the patient's usual daily activities

##### 11.4.3.3. Action Taken with TEGSEDI

Action taken with TEGSEDI due to the event is characterized by one of the following.

- **None:** No changes were made to TEGSEDI administration
- **Not Applicable:** SAE/AE was reported prior to TEGSEDI administration
- **Permanently Discontinued:** TEGSEDI was discontinued and not restarted
- **Temporarily Interrupted, Restarted – Same Dose:** Dosing and/or dosing frequency was temporarily interrupted/changed or delayed due to the AE and restarted at the same dose

#### ***11.4.3.4. Treatment Given for Adverse Event***

Any treatment (e.g., medications or procedures) given for the AE should be recorded on the AE eCRF. Treatment should also be recorded on the concomitant treatment or ancillary procedures eCRF, as appropriate.

#### ***11.4.3.5. Outcome of the Adverse Event***

If the event is a non-serious AE, then the event's outcome is characterized by one of the following:

- **AE Persists:** Patient terminates from the trial and the AE continues
- **Recovered:** Patient recovered completely from the AE
- **Became Serious:** The event became serious (the date that the event became serious should be recorded as the Resolution Date of that AE and the Onset Date of the corresponding SAE)
- **Change in Severity (if applicable):** AE severity changed

If the event is an SAE, then the event's outcome is characterized by one of the following:

- **Ongoing:** SAE continuing
- **Persists (as non-serious AE):** Patient has not fully recovered but the event no longer meets serious criteria and should be captured as an AE on the non-serious AE eCRF (the SAE resolution date should be entered as the date of onset of that AE)
- **Recovered:** Patient recovered completely from the SAE (the date of recovery should be entered as the SAE resolution date)
- **Recovered with Sequelae:** The signs/symptoms of the reported SAE have improved but not completely resolved, and a new baseline for the patient is established since full recovery is not expected
- **Fatal:** Patient died (the date of death should be entered as the SAE resolution date)
- **Unknown:** The outcome of the reported SAE is not available, e.g., patient is lost to follow-up

#### ***11.4.3.6. Follow-up of Adverse Event***

##### **Investigator Follow-Up**

During the study period, the investigator should follow each AE until the event has resolved to baseline grade or better, the event is assessed as stable, the patient is lost to follow-up, or the patient withdraws consent. Every effort should be made to follow all SAEs, AESIs, considered to be related to TEGSEDI or related to study procedures until a final outcome can be reported.

Resolution of AE (with dates) should be documented on the AE eCRF and in the patient's medical record.

The investigator should follow up or support the Sponsor's effort to follow up with all pregnancies reported during the study from either the study patient or the female partner of male study patient until pregnancy outcome is available. If the pregnancy results in the birth of a child, the mother and infant may continue to be followed for up to 8 weeks after birth.

## Sponsor Follow-Up

For SAEs, AESI and pregnancy cases in any patient who has completed or terminated study, the Sponsor or a designee should follow-up by telephone, fax, email, and/or a monitoring visit to obtain additional case details and outcome information (e.g., from hospital discharge summaries, consultant reports, autopsy reports, pregnancy status/outcome, new born status, etc.) in order to perform an independent medical assessment of the reported case.

## 11.5. Procedures for Handling Special Situations

### 11.5.1. Abnormalities of Laboratory Tests

Clinically significant abnormal laboratory test results may, in the opinion of the investigator, constitute or be associated with an AE. Examples of these include abnormal laboratory results that are associated with symptoms, or require treatment, e.g., bleeding due to thrombocytopenia, tetany due to hypocalcemia, or cardiac arrhythmias due to hyperkalemia. Whenever possible, the underlying diagnosis should be listed in preference to abnormal laboratory values as AEs. Clinically significant abnormalities will be monitored by the investigator until the parameter returns to its baseline value or until agreement is reached between the investigator and Sponsor. Laboratory abnormalities deemed not clinically significant (NCS) by the investigator should not be reported as AEs. Similarly, laboratory abnormalities reported as AEs by the investigator should not be deemed NCS.

The investigator is responsible for reviewing all laboratory reports. The clinical laboratory reports will serve as source documents and should include the investigator's assessment of clinical significance of out of range/abnormal laboratory values. If the lab results are electronically received, the investigator should assess clinical significance and document the assessment in the patient medical record.

### 11.5.2. Prescheduled or Elective Procedures or Routinely Scheduled Treatments

A prescheduled or elective procedure or a routinely scheduled treatment will not be considered an SAE, even if the patient is hospitalized; the study center must document all of the following:

- The prescheduled or elective procedure or routinely scheduled treatment was scheduled (or was on a waiting list to be scheduled) prior to obtaining the patient's consent to participate in the study
- The condition that required the prescheduled or elective procedure or routinely scheduled treatment was present before and did not worsen or progress in the opinion of the investigator between the patient's consent to participate in the study and the timing of the procedure or treatment
- The prescheduled or elective procedure or routinely scheduled treatment is the sole reason for the intervention or hospital admission

### 11.5.3. Dosing Errors

TEGSEDI treatment errors occurring during the study visit (including overdose, underdose, and administration error) should be documented as Protocol Deviations. A brief description should be

provided in the deviation, including whether the patient was symptomatic (list symptoms) or asymptomatic, and the event accidental or intentional.

Dosing details should be captured on the Dosing eCRF. If the patient takes a dose of TEGSEDI that exceeds protocol specifications and the patient is symptomatic, then the symptom(s) should be documented as an AE and be reported per [Section 11.4](#).

Dosing errors occurring between study visits will be reported by the patient and recorded in the eCRF; however, these dosing errors will not be considered a protocol deviation.

An overdose is the accidental or intentional use of a drug in an amount higher than the dose being studied. An overdose or incorrect administration of study treatment is not itself an AE, but it may result in an AE. All AEs associated with an overdose or incorrect administration of TEGSEDI should be recorded on the AE eCRF. If the associated AE fulfills seriousness criteria, the event should be reported to the Sponsor immediately (i.e., no more than 24 hours after learning of the event).

**Should an overdose occur,** the investigator or designee should contact the Sponsor or designee within 24 hours.

#### **11.5.4. Contraception and Pregnancy**

Male patients and female patients of childbearing potential must continue to use appropriate contraception with their partners or refrain from sexual activity.

If a patient becomes pregnant or a pregnancy is suspected, or if a male patient makes or believes that he has made someone pregnant during the study, then the study center staff must be informed immediately. An Initial Pregnancy Form should be submitted to the Sponsor or designee within 24 hours of first learning of the occurrence of pregnancy. Follow-up information including delivery or termination is reported on Follow-up Pregnancy Forms and reported within 24 hours.

Payment for all aspects of obstetrical care, child or related care will be the patient's responsibility.

Female patients: If a suspected pregnancy occurs while on the study (including follow-up), a pregnancy test will be performed. The patient with a confirmed pregnancy will be immediately withdrawn from treatment with TEGSEDI. However, the patient will be encouraged to complete the post-treatment follow-up period of the study to the extent that study procedures do not interfere with the pregnancy. Regardless of continued study participation, the pregnancy will be followed until the outcome of the pregnancy is known (i.e., delivery, elective termination, or spontaneous abortion). If the pregnancy results in the birth of a child, the study center and Sponsor may require access to the mother's and infant's medical records for an additional 8 weeks after birth.

Male patients: The progress of the pregnancy in a male patient's partner should be followed until the outcome of the pregnancy is known (i.e., delivery, elective termination, or spontaneous abortion). If the pregnancy results in the birth of a child, additional follow-up information may be requested for the mother and infant. Follow-up will be performed to the extent permitted by applicable regulations and privacy considerations.

**12. Plans for Disseminating and Communicating Study Results**

The results of this study will be summarized in a study report that, after review and approval by the sponsor, will be communicated to the US Food and Drug Administration (FDA) and Health Canada within the agreed timeframe.

## 1 List Of Abbreviations And Definitions Of Terms

Term	Definition
ADA	Anti-drug antibody
AE	Adverse event
AESI	Adverse events of special interest
ATTR	Transthyretin-mediated amyloidosis
CI	Confidence interval
CPM	Canadian Product Monograph
CRP	C-reactive Protein
eCRF	Electronic case report form
EDC	Electronic data capture
ESR	Erythrocyte sedimentation rate
ET	Early termination
GM-CSF	Granulocyte-macrophage colony stimulating factor
hATTR-PN	Polyneuropathy of hereditary transthyretin-mediated amyloidosis
ICF	Informed consent form
IFN	Interferon
Ig	Immunoglobulin
IL	Interleukin
MCP	Membrane cofactor protein
MedDRA	Medical Dictionary for Regulatory Activities
MIP	Macrophage inflammatory protein
PT	Preferred term
SAE	Serious adverse event

 	
Title: Statistical Analysis Plan
 
Program Name: "A Phase 4 Safety Study Assessing the Adverse Events Occurring Within 24 Hours of TEGSEDI Administration in Patients with polyneuropathy of Hereditary Transthyretin-mediated Amyloidosis (hATTR-PN)"
 
Protocol #: TEG4004
 
[REDACTED]
 
Version: Final 2.0 Effective Date: 06 October 2023

--	--

Term	Definition
SD	Standard deviation
SE	Standard error
SOC	System organ class
TEAE	Treatment emergent adverse event
TNF- $\alpha$	Tumor necrosis factor-alpha
TTR	Transthyretin
US	United States
USPI	United States Prescribing Information

## 2 Introduction

This document outlines the statistical methods to be implemented within the scope of Protocol TEG4004: A Phase 4 Safety Study Assessing the Adverse Events Occurring Within 24 hours of TEGSEDI Administration in Patients with Polyneuropathy of Hereditary Transthyretin-mediated Amyloidosis (hATTR-PN) version 3.0, 23 May 2023.

### 3 Study Objectives

The objective of the study is to characterize adverse events (AEs) occurring within 24 hours of TEGSEDI administration in adult patients with hATTR-PN and in individual patients with respect to time course of AE onset, vital sign changes, preventive measures, treatment required, risk factors, and subsequent adverse outcomes.

The endpoints of the study are AEs occurring within the first 24 hours of TEGSEDI administration at study visits, changes in vital signs and cytokines and inflammatory markers 24-hour post-injection with additional assessments of:

- Preventive measures used prior to the injection
- Treatment of AEs post 24 hour injection of TEVESDI at study visits
- Identification of risk factors for AEs occurring within the first 24 hours of TEVESDI administration at study visits
- Correlation of subsequent adverse outcomes

## 4 Overall Study Design

An open-label, phase 4, multicenter safety study in at least 75 patients with hATTR-PN prescribed 284 mg of TEGSEDI in the US (United States) and Canada.

## 5 Selection of Study Population

This study will be conducted at multiple study centers in the US and Canada. TEGSEDI will be prescribed to the patient by the healthcare provider prior to enrolling in this study. TEGSEDI will be administered from approved packaged and labeled packs. Used syringes will be disposed of per the product's instructions for use.

## 5.1 Patient Inclusion Criteria

To be eligible to enroll in this study, patients must meet the following eligibility criteria:

 	
Title: Statistical Analysis Plan
 
Program Name: "A Phase 4 Safety Study Assessing the Adverse Events Occurring Within 24 Hours of TEGSEDI Administration in Patients with polyneuropathy of Hereditary Transthyretin-mediated Amyloidosis (hATTR-PN)"
 
Protocol #: TEG4004
 
[REDACTED]
 
Version: Final 2.0 Effective Date: 06 October 2023

--	---

1. Satisfy one of the following:
  - a. US Patients: Adult patients ( $\geq 18$  years old) diagnosed with hATTR-PN and prescribed TEGSEDI according to the USPI (United States Prescribing Information)
  - b. Canadian Patients: Adult patients ( $\geq 18$  years old) diagnosed with stage 1 or stage 2 hATTR-PN and prescribed TEGSEDI according to the CPM (Canadian Product Monograph) (TEGSEDI CPM)
2. Must have given written informed consent for participation in this study
3. Must provide access to their previous medical records
4. Are about to initiate or have initiated treatment with TEGSEDI
5. Be willing to complete required testing and report any AEs and/or changes in medications
6. Satisfy one of the following:
  - a. Females: Non-pregnant and non-lactating; abstinent, or if engaged in sexual relations and of childbearing potential, patient is using an acceptable contraceptive method from time of signing the ICF (Informed consent form) until 13 weeks after the last dose of TEGSEDI administration
  - b. Males: Abstinent or if engaged in sexual relations with a female of childbearing potential, patient is utilizing an acceptable contraceptive method from the time of signing the ICF until 13 weeks after the last dose of TEGSEDI administration

**Notes:**

- a) If a patient has started TEGSEDI and then stops and restarts at a later date, they can be enrolled in the study upon re-starting if they meet the inclusion criteria above
- b) Patients may participate in both studies TEG4004 and TEG4001
- c) Patients with any stage of disease can be enrolled provided they meet the inclusion criteria specified above
- d) Patients with a history of prior liver transplant may be enrolled

 	
Title: Statistical Analysis Plan
 
Program Name: "A Phase 4 Safety Study Assessing the Adverse Events Occurring Within 24 Hours of TEGSEDI Administration in Patients with polyneuropathy of Hereditary Transthyretin-mediated Amyloidosis (hATTR-PN)"
 
Protocol #: TEG4004
 
[REDACTED]
 
Version: Final 2.0 Effective Date: 06 October 2023

--	---

e) Patients with transplanted liver with amyloidogenic mutation (associated with amyloid formation) are considered to have ATTR (Transthyretin-mediated amyloidosis) and therefore these patients can enter the study

## 5.2 Patient Exclusion Criteria

None

## 6 Schedule of Assessments

The study will consist of a Screening/Qualification period, a Treatment period and Post-Treatment Follow-up period as per Table 1 and Table 2.

The Screening/Qualification period is defined as the interval of time from the signing of informed consent until the first on-study dose of TEGSEDI.

The treatment period begins at the time of the first on study TEGSEDI administration and the end of treatment period is defined as follows:

- For patients who complete treatment with TEGSEDI on study, the last observation in the treatment period will be the 20-30 hour post-injection visit of the last administered TEGSEDI dose on study. If the time of the last TEGSEDI dose is missing, or the time of the assessment in question is missing, the assessment will be included in the treatment period if it occurred on the same day or one day subsequent to the last dose of TEGSEDI
- For patients who discontinue TEGSEDI or withdraw from the study and continue with TEGSEDI outside the study, the early termination (ET) visit will serve as the end of the treatment period

For patients who discontinue TEGSEDI, the post treatment follow-up period begins after the end of the treatment period, as defined above, and ends with the last available data collected per the clinical trial protocol. Data for the post-treatment follow-up period will be analyzed and summarized separately for patients who develop a hypersensitivity reaction.

	Title: Statistical Analysis Plan				
	Program Name: "A Phase 4 Safety Study Assessing the Adverse Events Occurring Within 24 Hours of TEGSEDI Administration in Patients with polyneuropathy of Hereditary Transthyretin-mediated Amyloidosis (hATTR-PN)"				
	Protocol #: TEG4004				
	[REDACTED]				
	Version: Final 2.0 Effective Date: 06 October 2023				

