#### **9.1.4. Discontinuation of TEGSEDI**

If a patient discontinues TEGSEDI for a reason other than a hypersensitivity reaction, the patient will have an ET visit as soon as possible after the decision to end treatment and will be followed for 8 weeks after treatment discontinuation for AEs assessments, changes in vital signs and laboratory sampling.

If a patient discontinues TEGSEDI due to hypersensitivity, the patient will undergo an ET visit and an 8-week follow-up visit. He/she will also return for additional ADA testing at 4 months after the hypersensitivity reaction, and then again at 8 months and 12 months after the hypersensitivity reaction, if the study is still ongoing (see definition of [Milestones for Study End](#)).

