### **9.6.4. Safety Analysis**

Patient incidence rates of all AEs will be tabulated by Medical Dictionary for Regulatory Activities (MedDRA) system organ class (SOC), and by MedDRA preferred term (PT). Narratives of deaths, all discontinuations, serious AEs, pregnancies and AEs of special interest (AESI) will also be provided.

All treatment emergent AEs, all treatment emergent AEs potentially related to TEGSEDI, all treatment emergent serious AEs, and all treatment emergent serious AEs potentially related to TEGSEDI will be summarized.

Incidence (95% confidence interval) of AEs occurring within 1 day of TEGSEDI administration, and time to onset from TEGSEDI injection and duration of these AEs will be summarized by visit and overall in any visit. The rates of AEs during the 1-day visit occurring after preventive measures will also be summarized. Resolution time with and without treatment administered for the AEs will be summarized.

For each study visit on treatment, the result and change from pre-dose baseline in vital signs (body temperature, heart rate, respiratory rate, and systolic, diastolic blood pressure) and cytokines/inflammatory markers will be summarized using descriptive statistics for all patients in the Evaluable Set and by presence/absence of AEs within 1 day of TEGSEDI administration.

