**Table 1. Schedule of Assessments for Patients Who do not Develop a Hypersensitivity Reaction**

Study Periods	Screening 	Treatment Period				Post-Treatment Follow-up (Patients who discontinued TEGSEDI) 8-weeks (+/- 1 week) 
		Initial Treatment Visit (Month 0) and Every 4 months Visit (+/- 2 weeks) for 12 months		End of Study Visit		
Procedures and Testing	-2 to 0 weeks prior to first study injection	Pre-injection	Post injection 1-hour ± 15 mins 2-hour ± 15 mins 4-hour ± 30 mins 8-hour ± 30 mins 20-30 hours	Pre-injection	Post injection 1-hour ± 15 mins 2-hour ± 15 mins 4-hour ± 30 mins 8-hour ± 30 mins 20-30 hours	Early Termination Visit 
Informed Consent	X					
Demographics	X					
Medical History	X					
Full Physical Examination 	X					
Abbreviated Physical Examination 		X 		X		X X
Height	X					
Weight	X	X 		X		X X
Vital Signs	X	X	X	X	X	X X
Urine Pregnancy Testing	X 	X 		X 		X 
IgE, IgG, IgM		X	X	X	X	X

	Title: Statistical Analysis Plan
	Program Name: "A Phase 4 Safety Study Assessing the Adverse Events Occurring Within 24 Hours of TEGSEDI Administration in Patients with polyneuropathy of Hereditary Transthyretin-mediated Amyloidosis (hATTR-PN)"
	Protocol #: TEG4004
	[REDACTED]
	Version: Final 2.0 Effective Date: 06 October 2023

Inflammatory Markers		X	X	X	X	X	
Samples for Possible Future Testing		X	X	X	X	X	X
ADA		X 		X		X 	
Adverse Events Post Injection at Study Visit			X		X		
Concomitant Medications	X	X		X		X	X

1. The Screening visit and the Month 0 visit can occur on the same day.
2. The Physical Examination and Weight does not need to be completed at the Month 0 study visit if they were performed during Screening.
3. If the patient withdraws from the study, the patient should return for an ET visit within 2 weeks after the decision to withdraw from the study. If the patient discontinues TEGSEDI, they should have an ET visit within 2 weeks of the decision to end treatment and one follow-up visit 8-weeks ( $\pm$  1 week) after their last dose of TEGSEDI. If the ET and the 8 week follow up visit are within 2 weeks of each other, the assessments can be combined.
4. Urine pregnancy testing is only for women of childbearing potential as defined in the protocol.
5. The baseline ADA sample is only drawn at the Month 0 visit.

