## 8.2.2 Adverse Events

### 8.2.2.1 Treatment-emergent Adverse Events (TEAEs)

TEAEs are defined as AEs with an onset date/time on or after the date/time of the first on study administration of TEGSEDI. Related TEAEs are TEAEs with a reported relationship of "Possible" or "Related". TEAEs with a missing relationship will also be counted as Related. Serious Adverse Events (SAEs) will be indicated as such in the eCRF and can be defined as treatment emergent, based on when the SAE initiated. AEs will be summarized using the safety set for the treatment period among both patients who develop a hypersensitivity reaction and those patients who do not develop a hypersensitivity reaction.

TEAEs will be summarized as follows:

- Overview of Treatment-emergent AEs
- Treatment-emergent AEs by System Organ Class and Preferred Term
- Treatment-emergent AEs by System Organ Class, Preferred Term and Severity
- Treatment-emergent AEs Related to TEGSEDI by System Organ Class and Preferred Term
- Treatment-emergent AEs Related to TEGSEDI by System Organ Class, Preferred Term and Severity
- Treatment-emergent Adverse Events of Special Interest (AESI) by System Organ Class and Preferred Term

 	
Title: Statistical Analysis Plan
 
Program Name: "A Phase 4 Safety Study Assessing the Adverse Events Occurring Within 24 Hours of TEGSEDI Administration in Patients with polyneuropathy of Hereditary Transthyretin-mediated Amyloidosis (hATTR-PN)"
 
Protocol #: TEG4004
 
[REDACTED]
 
Version: Final 2.0 Effective Date: 06 October 2023

--	---

- Treatment-emergent AESIs by System Organ Class, Preferred Term and Severity
- Treatment-emergent Serious AEs by System Organ Class and Preferred Term
- Treatment-emergent Serious AEs Related to TEGSEDI by System Organ Class and Preferred Term
- Treatment-emergent AEs leading to discontinuation of TEGSEDI by System Organ Class and Preferred Term

AEs will also be presented in data listings as follows:

- Listing of All Adverse Events
- Listing of Adverse Events Leading to Discontinuation
- Listing of Serious Adverse Events
- Listing of Adverse Events of Special Interest

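### For patients who discontinue, the SAP's main TEAE tables stop at the Early Termination visit, and no adverse event table is named for the follow-up after it

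*Combined protocol and SAP*

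**What the plan says.** **SAP 8.2.2.1** defines TEAEs with a start and no end: "TEAEs are defined as AEs with an onset date/time on or after the date/time of the first on study administration of TEGSEDI". The same section then sets the period for its tables: "AEs will be summarized using the safety set for the treatment period among both patients who develop a hypersensitivity reaction", and likewise patients without one. The list that follows covers SOC/PT, severity, related, special-interest (AESI), serious and discontinuation tables.

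**SAP 6** closes the treatment period. For patients who stop TEGSEDI, or who leave the study but stay on the drug, "the early termination (ET) visit will serve as the end of the treatment period". For those who stop the drug, a post-treatment follow-up period begins at that point. Its data are covered by one sentence: "Data for the post-treatment follow-up period will be analyzed and summarized separately for patients who develop a hypersensitivity reaction". Section 8.2.2 names no AE table for that period.

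**SAP Table 1, footnote 3** gives the visit timing for patients who stop the drug: "they should have an ET visit within 2 weeks of the decision to end treatment and one follow-up visit 8-weeks" after the last dose, with a window of 1 week either side. ET and follow-up assessments may be merged if the two visits are within 2 weeks of each other.

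**Protocol v2.0** is broader. Section 9.6.4 says: "Patient incidence rates of all AEs will be tabulated", with no limit on period. Under section 9.1.4, a patient who stops for a reason other than hypersensitivity "will be followed for 8 weeks after treatment discontinuation for AEs assessments". Section 9.2.2.1.4 lists AEs since the previous visit among the procedures at both the ET and the 8-week visit.

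**The concern.** A serious, special-interest or related event that starts after ET in a patient who has stopped TEGSEDI meets the TEAE definition but falls outside the period its tables cover. A programmer who follows the definition counts it; one who follows the sentence that introduces the tables does not. Followed as written, that sentence excludes the event.

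The denominator is the safety set and does not change. Excluding events that start after ET can therefore only lower a patient-incidence figure or leave it as it is. The study's stated objective includes later adverse outcomes, and protocol 9.6.4 promises rates, which a listing does not give. The annual-report tables in SAP 9 of related TEAEs, serious TEAEs and AESIs carry no treatment-period limit, so they could also disagree with the main tables under similar titles.

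**Working it through.** The documents give no figure on this point. Their one statistical figure, 95% probability of seeing an AE of 4% incidence in 75 patients, reproduces as 1 − 0.96^75 = 0.953 and has no bearing here.

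**Who is affected.** Only patients who stop TEGSEDI. Patients who leave the study but stay on the drug have no visit after ET, and the treatment period of those who complete treatment ends at the 20-30 hour assessment of the last on-study dose.

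**Inputs**
- F, the follow-up visit in weeks after the last dose: 8, range 7 to 9 (SAP Table 1, footnote 3).
- E, the ET visit in weeks after the last dose: not given. ET is timed from the decision to stop, and the gap between last dose and decision is not stated. E is therefore an assumption, shown over a range.

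**Share of the follow-up that lies after ET** = (F − E)/F.

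| ET, weeks after last dose (E) | Follow-up at week 8 | Share after ET |
|---|---|---|
| 1 | 7/8 | 87.5% |
| 2 | 6/8 | 75% |
| 3 | 5/8 | 62.5% |
| 4 | 4/8 | 50% |
| 6, visits kept separate | 2/8 | 25% |
| Visits combined at week 8 | 0/8 | 0% |

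With E = 2 and the 1-week window, the share runs from 5/7 = 71% to 7/9 = 78%. More than half lies after ET as long as ET comes before week 4.

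**Effect on a table row.** A patient changes a row only if that patient's first qualifying event for the row starts after ET. If the safety set has the planned minimum of 75 patients, each such patient is worth 1/75 = 1.3 percentage points. The documents do not say how many there would be.

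**The case against.** Four points on the other side carry weight.

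1. *Follow-up may already be meant for everyone.* A reader might infer from SAP 6 that follow-up data are summarised only for hypersensitivity patients. The text does not say so. The follow-up period is defined for all who discontinue, and summarising one group separately can mean a split by hypersensitivity status, which would suit the different visit schedules. SAP 8.2.3 gives a follow-up change rule for vital signs without that restriction, and 8.2.4 extends it to cytokines and inflammatory markers. This stands, but 8.2.2 has no matching rule for AEs in either group.

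2. *The events are not lost.* A reader might also infer that they appear in no table. That is not established. The annual-report tables may include them, and the mock tables (SAP Appendix B) are not available to check. Listings of all AEs, SAEs and AESIs run on the safety set, and protocol 9.6.4 requires narratives for deaths, discontinuations, SAEs and AESIs. This stands too. What is missing is their place in the main incidence tables.

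3. *The protocol version differs.* The SAP is written for protocol v3.0, which is not supplied. SAP Tables 1 and 2 lack the v2.0 row for AEs since the last visit, and their one AE row covers post-injection time points. Whether AEs are still collected at the ET and follow-up visits is therefore open. This limits the claim of conflict to v2.0. It does not remove the gap, because the SAP keeps both the visit and the follow-up period.

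4. *The main endpoint is untouched.* The objective concerns AEs within 24 hours of dosing, and an on-treatment AE table is a legitimate choice. Both are true, so the remedy is to add to those tables, not replace them.

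**Conclusion.** The point holds as a mismatch between stated rules. The main TEAE tables end at the ET visit for discontinuers, the TEAE definition does not end there, and no follow-up AE table is named for either hypersensitivity group. This is narrower than protocol v2.0, sections 9.6.4 and 9.1.4. Serious, AESI and related events that start after ET are left out of the main incidence tables, though not out of the listings and narratives.

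The size is conditional. Most of the 8 weeks is affected if ET comes within 1 to 3 weeks of the last dose, much less if ET is late, and none if the visits are combined. A reader might take three quarters as a fixed share, since 8 − 2 = 6 weeks. That assumes that the decision to stop coincides with the last dose and that ET uses its full 2-week allowance; the documents state neither. They also give no discontinuation rate, so no count of patient-weeks or events can be supported. Nor do they show that incidence will in fact be lowered, only that it cannot be raised.

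The change should be made before the final tables are produced. It does not affect the 24-hour analysis or the sample size.

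**What to change.** - **SAP 8.2.2.1:** state an end point for TEAEs. Keep the treatment-period tables. Add the SOC/PT, serious, AESI and related tables for the treatment period plus post-treatment follow-up, covering all discontinuers.
- **SAP 6:** state that follow-up summaries cover all discontinuers, split by hypersensitivity yes/no.
- **SAP Tables 1 and 2:** reconcile with the protocol in force on whether AEs are collected at the ET and follow-up visits. If collection there has been dropped, say so, and set the TEAE end point to match.

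The cost is SAP wording and repeat runs of existing tables. Where AEs are already recorded at these visits, no new data are needed.
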